Patients with neuropsychological diagnoses are reported to be more likely to develop severe COVID-19 disease. Previous work has shown an increased incidence of severe respiratory infection and worse critical care outcomes associated with pharmacological neuropsychological treatments. It remains unclear whether particular conditions or treatments predispose to severe COVID-19 disease (requiring hospital, critical care admission or death) more than to other acute respiratory infections. Patients with COVID-19 disease are reported to subsequently have a high incidence of neuropsychological disease. However, the incidence of neuropsychological sequelae is also high following other critical illness. It is unclear whether neuropsychological sequelae following severe COVID-19 disease are more serious or managed differently than following other severe acute respiratory infection (SARI) such as bacterial or viral pneumonia, particularly when accounting for risk factors associated with the disease.

Antecedent analysis

We will explore the associations between pharmacological treatments (hypnotics and anxiolytic, antidepressant, drugs used in psychoses and related disorders) of preexisting neuropsychological diagnoses (anxiety, mood, psychotic disorders, or dementia), and severe clinical outcomes of COVID-19 infection (hospital admission, ICU admission and death) in comparison to those not receiving such treatments.

We will determine whether the associations between pre-existing neuropsychological treatments and severe clinical outcomes differ for patients with COVID-19 infection in comparison to patients with non-COVID-19 severe acute respiratory infections (SARI)

Sequelae analysis

We will determine the risks of receiving a new neuropsychological diagnosis or new neuropsychological medication within one year after discharge from hospital for patients admitted with COVID-19 infection in comparison to patients with non-COVID-19 severe acute respiratory infections (SARI) investigating the subgroups of hospitalised patients admitted to and not admitted to an ICU.

INTRODUCTION

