Patients with underlying psychological illness have been reported to be at significantly greater risk of infection with and death from COVID-19 [1–3]. Previous work suggests specific drug classes, such as antipsychotics and antidepressants, are associated with an increased risk of respiratory infection, and death associated with that infection [4–6], though these findings may be associated with significant residual confounding [5]. Whether the associations of psychological illness with infection and death from SARS-COVID-19 are related to particular medication classes has not so far been determined.

Psychological illness prior to ICU admission has been poorly studied. However, use of Selective Serotonin Reuptake Inhibitors (SSRIs) prior to ICU admission has been associated with increased mortality, an effect related to the degree of re-uptake inhibition [7]. Whether prior psychological illness and use of particular classes of medication for these diseases is associated with ICU admission or outcome, either with COVID-19 or other severe acute respiratory infection has not been studied.

Previous SARS outbreaks have been associated with significant neuropsychological sequelae [8] In the United States, recent work has suggested that COVID-19 disease is associated with significant subsequent neuropsychological disease [3].

Prior to the COVID-19 outbreak, patients who have been admitted to an ICU had high incidences of subsequent neuropsychological sequelae [9] and ongoing cognitive impairment [10]. However, understanding the neuropsychological consequences of critical illness has been impaired by limited understanding of prior neuropsychological disease [11]. We will investigate whether neuropsychological sequelae of patients treated on an ICU with COVID-19 disease differ from those treated on ICU for different conditions, taking into account prior neuropsychological disease.

Hypothesis

We hypothesise that prior neuropsychological disease increases the risk of severe COVID-19 outcomes as with other acute respiratory disease and that this increase is associated with treatment with particular medication classes.

We hypothesise that infection with COVID-19 results in severe neuropsychological outcomes following treatment in hospital or on an ICU and that these outcomes differ in type and severity from neuropsychological outcomes seen following admission for SARI.

Aims

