A retrospective cohort data linkage study of patients aged 18 years and above registered in English general practices. This protocol is written following RECORD guidance [12].

Settings Describe the setting, locations, and relevant dates, including periods of recruitment, exposure, follow-up, and data collection.

1205 general practices in England contributing to the QResearch database, which is nationally representative. We defined cohorts during the COVID pandemic as between 24th January 2020 (the date of the first confirmed COVID-19 case in England) and study end (30th June 2021). We defined retrospective comparison cohorts as the 5 years prior to this date (24th January 2015- 23rd January 2020).

Data linkage

The study will include adult patients registered with the QResearch database. Practices must have been contributing to the QResearch database for at least 12 months. For the investigation of associations of pre-existing neuropsychological diseases and treatments (cohort 1) patients must be registered for at least a 12-month period before 24th January 2020. For the investigation of incidence of new neuropsychological diseases (cohort 2) patients must be registered for at least a 12-month period between January 2015 to 2020. The date of study entry is separately defined below for each study cohort.

Patients in QResearch will be linked to: (1) the ICNARC Case Mix Programme (CMP) database, the national clinical database from adult critical care; (2) the Hospital Episode Statistics (HES) data warehouse containing records of all patients admitted to NHS hospitals and Emergency departments in England; (3) the national registry of COVID-19 RT-PCR positive test results from Public Health England (PHE); and (4) Office of National Statistics COVID-19 mortality data, which includes all deaths due to COVID-19 in England. Data linkage will be based primarily on NHS number. For a description of the datasets see Supplemental material S1.

Participants

Give the eligibility criteria, and the sources and methods of selection of participants. Describe methods of follow-up. The methods of study population selection (such as codes or algorithms used to identify subjects) should be listed in detail.

Aim 1.

From the linked dataset, we will extract two cohorts to explore the association between neuropsychological diseases and treatments and hospitalisation, ICU admission or death:

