 Cohort one is adult patients aged 18 years of age or over on 24th January 2020 (the study entry date, when the first confirmed COVID-19 case occurred in the UK) who were registered in a primary care practice within the QResearch programme on or before 24th January 2019. Patients will be followed-up from study entry date until development of severe COVID-19 disease, defined as the first date of either hospitalisation, ICU admission, or death. Patients will be censored at the first occurrence of deregistration from the GP practise, death, or date of the final data extract from the linked datasets.

Cohort two is an open cohort of patients aged 18 years of age or over (including those who become 18 within this period) who had been registered with a primary care practise within the QResearch database for at least one year, between 24th January 2015 and 23rd January 2020. For each patient, the earliest day on which all these conditions were met will be defined as their study entry date, and they will be followed-up until development of severe disease due to SARI, defined as hospitalization, ICU admission, or death. Patients will be censored at the earliest of first occurrence of deregistration from the GP practise, death from other causes, 24th January 2020 or date of the final data extract from the linked datasets.

Aim 2.

- Cohort three will include adult patients (aged 18+ on date of hospital admission) discharged alive following a hospital admission including an ICU admission resulting from COVID -19 infection (defined below) between 24 January 2020 and study end date, who were registered in a primary care practice within the QResearch programme before their ICU admission. It will be used to evaluate the risk of subsequent neuropsychological sequalae from the date of discharge. Patients will be censored at the earliest of first occurrence of deregistration from the GP practice, death from other causes, 12 months post discharge from hospital, or date of the final data extract from the linked datasets.

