- Cohort four will include adult patients (aged 18+ on date of hospital admission) discharged alive following a hospital admission including an ICU admission resulting from SARI (defined below) admitted between 24 January 2015 and 23rd January 2020, who were registered in a primary care practice within the QResearch programme before their ICU admission. The cohort will allow comparisons to be made with cohort three. Follow-up will be from the date of discharge. Patients will be censored at the earliest of first occurrence of deregistration from the GP practise, death from other causes, 12 months post discharge from hospital or date of the final data extract from the linked datasets.
- Cohort 5 will include adult patients (aged 18+ on date of hospital admission) discharged alive following a hospital admission including an ICU admission resulting from SARI (defined below) between 24 January 2020 and study end date, who were registered in a primary care practice within the QResearch programme before their ICU admission. It will be used to allow comparison with cohort 3. Patients will be censored at the earliest of first occurrence of deregistration from the GP practice, death from other causes, 12

months post discharge from hospital, or date of the final data extract from the linked datasets.

Variables

Definition of outcomes Aim 1

For cohort one, our primary outcome is the first occurrence of any one of the following:

1. Hospital admission resulting from COVID-19 infection defined as testing positive for SARS-CoV-2 (as recorded in the PHE database) in the 14 days prior to or during a hospital admission period in the HES dataset, or having an ICD10 code U07.01 for confirmed COVID-19 diagnosis in that HES admission record

2. Admission to an ICU resulting from COVID-19 infection which will be defined as patients admitted to an ICU within the ICNARC dataset of COVID-19 admissions.

3.All - cause mortality following COVID-19 infection.

Secondary outcomes are each of the three events defined above, considered separately (i.e. COVID-19 hospital admissions; ICU admission; death).

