For cohort two, our primary outcome is the first occurrence of either hospital admission with SARI in the HES dataset (defined as a new ICD-10 code J09-J22 in the HES dataset) or ICU admission in the ICNARC CMP dataset with SARI (defined as any admission with unique diagnostic code any one of RE129 RE131 RE82 RE50 RE86 RE94 RE75 RE133 RE132 RE121 RE1 RE128 RE16 RE130 RE117 RE42 RE41) or death. Secondary outcomes will be each of these three events considered separately (I.e. SARI related hospital admission, ICU admission, death).

Aim 2.

Our primary outcome is development of new neuropsychological disease up to 1 year following hospital discharge which we define as having received a diagnostic code as below:

- Anxiety and stress-related disorders [ICD F40-48 and corresponding Read codes]
- Mood disorders [ICD F30-39 and corresponding Read codes]
- Psychotic disorders [ICD F20-29 and corresponding Read codes]
- Dementia [ICD F00-F03, G30, G31.0 ? and corresponding Read codes]

Secondary outcomes are the diagnosis of new neuropsychological disorders (as defined above) with treatment, and where numbers are available the new diagnosis with or without treatment of each class of disorders, each considered as a separate endpoint.

Neuropsychological treatments are defined as:

- Hypnotics and anxiolytics: (hypnotics, anxiolytics, barbiturates and methyprylone, benzodiazepines)
- Antidepressant drugs (Tricyclic and related antidepressant drugs, Monoamine-oxidase inhibitors, Selective serotonin re-uptake inhibitors, Other antidepressant drugs)
- Drugs used in psychoses and related disorders (Antipsychotic drugs and depot injections, Lithium salts, Phenothiazine derivatives)

Definition of exposures

Aim 1

Neuropsychological disease will be defined as an ordinal variable with the following three categories: no relevant diagnosis or drugs; diagnosis ever recorded without recent drug treatment; diagnosis present with recent drug treatment (with at least two prescriptions for neuropsychological treatments as above within the six months preceding study entry).

Our primary exposure is active neuropsychological disease on the study entry date which we define as having received a diagnostic code as above (24th January 2020 for cohort 1 and 24th January 2015 for cohort 2).

Aim 2.

The primary exposure is a hospital or ICU admission resulting from COVID-19 infection. Comparator exposures are hospital or ICU admission resulting from SARI.

Covariates

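### Aim 2 promises to account for prior neuropsychological disease, but its cohort definitions, outcome rule and covariate list neither exclude it nor adjust for it

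*Protocol*

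**What the plan says.** **Intent.** The Introduction says the ICU sequelae comparison will be made "taking into account prior neuropsychological disease", and the summary of potential impact repeats this. The Discussion faults earlier post-ICU work for not knowing patients' disease before admission.

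**Outcome.** Under the Aim 2 outcome definitions, the primary outcome is given as "development of new neuropsychological disease up to 1 year following hospital discharge which we define as having received a diagnostic code as below". Four diagnostic groups follow (anxiety and stress-related, mood, psychotic, dementia). Nothing says what makes a code new.

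**Eligibility.** Under Participants, Aim 2, cohorts 3, 4 and 5 each contain patients "who were registered in a primary care practice within the QResearch programme before their ICU admission". None gives a minimum duration of registration or excludes patients with earlier neuropsychological disease.

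**Look-back.** The Data linkage section does set a rule for the study of new disease: "patients must be registered for at least a 12-month period between January 2015 to 2020". It attaches this to cohort 2, which under Participants is an Aim 1 SARI cohort. The Figure 2 text uses that same label for the COVID sequelae cohort.

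**Adjustment.** Statistical Methods, Aim 2, adjusts for every covariate listed earlier; the Effect Modifiers section makes the same list optional. The list covers neurological conditions such as epilepsy and Parkinson's disease. It has no anxiety, mood or psychotic disorder, no dementia, and no hypnotic, antidepressant or antipsychotic. The propensity score under Sensitivity analyses draws on the same list. A three-level variable combining earlier diagnosis and recent treatment is defined, but only as the Aim 1 exposure.

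**Medication.** The opening summary gives the sequelae as "receiving a new neuropsychological diagnosis or new neuropsychological medication within one year after discharge from hospital". The Aim 2 outcomes count treatment only together with a new diagnosis.

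**The concern.** Followed as written, the outcome rule counts a depression code entered again at a GP visit after discharge, even if the depression is years old. The written model then has no term for earlier disease. Earlier disease is an obvious predictor of a later code, and it is already held in QResearch.

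Two things could go wrong. If the share of patients with earlier disease differs between the COVID and SARI cohorts, the hazard ratio mixes that difference with any effect of COVID-19. If the shares are equal, old disease still adds events that say nothing about incidence, and it can pull a real effect towards 1. Either way, the primary Aim 2 result would not measure what it is named for, on the very point the protocol presents as its advance over earlier work.

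**Working it through.** The protocol gives no power calculation, event rate or prior-disease prevalence for Aim 2, so there is no planned figure to reproduce. The main check is to set the text side by side; the arithmetic only shows what could follow.

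**1. Can the operative text identify new disease?**

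- Outcome: a listed code after discharge, with no condition on earlier codes.
- Eligibility: no exclusion for earlier codes in cohorts 3 to 5.
- Model and propensity score: no earlier diagnosis or psychotropic treatment among the covariates.

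None of the three carries out the stated intent.

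**2. Does the 12-month rule secure a look-back?** If it is meant for the sequelae cohorts, 12 months inside a January 2015 to 2020 window essentially precede any admission in cohorts 3 and 5, which start on 24 January 2020. Cohort 4 is different: a patient admitted early in 2015 could satisfy the rule with registration time after admission. The cohort definitions themselves repeat no such rule.

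**3. Confounding (all inputs assumed).** Let p3 and p4 be the shares with earlier disease in the COVID and SARI cohorts, and R the rate of receiving a code with versus without earlier disease. With a true hazard ratio of 1 and no adjustment:

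apparent HR ≈ [1 + p3(R − 1)] / [1 + p4(R − 1)]

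| p3 v p4 | R = 2 | R = 5 | R = 10 |
|---|---|---|---|
| 30% v 30% | 1.00 | 1.00 | 1.00 |
| 25% v 30% | 1.25/1.30 = 0.96 | 2.00/2.20 = 0.91 | 3.25/3.70 = 0.88 |
| 20% v 30% | 1.20/1.30 = 0.92 | 1.80/2.20 = 0.82 | 2.80/3.70 = 0.76 |
| 15% v 30% | 1.15/1.30 = 0.88 | 1.60/2.20 = 0.73 | 2.35/3.70 = 0.64 |

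Swapping the shares inverts the ratios, from 1.30/1.25 = 1.04 to 3.70/2.35 = 1.57. The formula ignores any partial control through listed covariates such as age, deprivation, alcohol intake and learning disability.

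**4. Dilution (all inputs assumed).** With 30% earlier disease in both cohorts, the share of counted events in patients with earlier disease is pR / (1 − p + pR):

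- R = 2: 0.6/1.3 = 46%
- R = 5: 1.5/2.2 = 68%
- R = 10: 3.0/3.7 = 81%

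If COVID-19 raises the rate 1.5-fold only in patients without earlier disease, the apparent ratio is [(1 − p) × 1.5 + pR] / [(1 − p) + pR]:

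- R = 2: 1.65/1.3 = 1.27
- R = 5: 2.55/2.2 = 1.16
- R = 10: 4.05/3.7 = 1.09

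**5. After the fix.** Restricting to patients with no earlier code gives 1.00 in step 3 and 1.50 in step 4 under this simple model. Adjustment alone would remove the confounding in step 3 but not the dilution in step 4.

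**The case against.** The strongest reply is that the intent is plain. The outcome uses the word new, the Introduction and impact summary promise to allow for earlier disease, and the exact washout rule is commonly left to a statistical analysis plan, which is not available here. The Aim 2 causal diagram (Figure 4) is also not shown and may include prior disease. This stands as far as intent goes: the issue is not ignored. It does not dispose of the point, because the protocol itself goes on to define the outcome and name the adjustment set, and neither carries out the intent. Nor does the planned E-value help: it addresses unmeasured confounding, and this variable is measured.

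A reader might infer that the protocol requires no look-back at all. The Data linkage section does not support that; it has a 12-month rule, and the fault is its label, its window and its absence from the cohort definitions.

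A reader might also infer that the hazard ratio will be confounded, and in COVID-19's favour. The documents do not support that either. Objective 3, which asks whether prior disease carries different risks of severe COVID-19 and of severe SARI, makes unequal shares plausible. But no prevalence is given, equal shares give no confounding from this source, and the direction could be reversed.

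Finally, excluding everyone with any earlier code narrows the question: new dementia after old anxiety would leave the primary outcome. That is a fair cost, and the reason to define class-specific endpoints by class.

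**Conclusion.** The point holds and should be corrected before analysis. The Aim 2 text as written can count re-recorded old disease as new and leaves earlier disease and treatment out of the main model and the propensity score, contrary to the protocol's own statements. The consequence is possible confounding or dilution of the COVID-versus-SARI hazard ratio.

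Its size and direction cannot be known from the protocol. The illustrative range of 0.64 to 0.96 under a true value of 1 rests on assumed shares of 15–25% against 30%, rate ratios of 2 to 10, and no partial control by other covariates. Equal shares give 1.00, with dilution as the remaining harm.

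The medication mismatch between the opening summary and the outcome definitions is a separate inconsistency and adds nothing to the case on prior disease.

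**What to change.** - **Outcome.** Define new disease as a qualifying code after discharge in a patient with no qualifying code before the index admission: no code in any of the four groups for the primary outcome, and none in the same group for class-specific endpoints.
- **Look-back.** Require at least 12 months' registration before the index admission in the definitions of cohorts 3, 4 and 5. Reconcile the Data linkage rule, its cohort label and the Figure 2 labels with the Participants section.
- **Adjustment.** Add the three-level diagnosis and treatment variable from Aim 1, measured at the index admission, to the Aim 2 covariates and the propensity score wherever patients with earlier disease or treatment remain in the analysis.
- **Separately,** reconcile new medication in the opening summary with the Aim 2 outcomes, either as an outcome in its own right or by removing it from the summary.

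The cost is mainly wording, since the data are already in QResearch. There will be fewer eligible patients and possibly far fewer counted events. Under the assumptions above, exclusion would remove between 0.30/1.15 = 26% (share 15%, R = 2) and 2.50/3.25 = 77% (share 25%, R = 10) of COVID events as now counted, and 46–81% of SARI events at a 30% share. The protocol already expects low event rates for Aim 2, so this loss should be stated openly.

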Royston Parmar flexible parametric survival models will be used to estimate the hazard ratio of severe COVID-19 outcome (hospital or critical care admission and death) in cohort 1 for patients with neuropsychological disease at study entry compared with those without disease, and for individual neuropsychological diseases and treatments.

This analysis will be adjusted for the listed covariates. The age variable will be included as a restricted cubic spline rather than a linear term. Before commencing analysis, we will assess the numbers of patients with each comorbidity, and may if necessary group the presence of certain less common comorbidities together. Any such grouping will be done on the basis of clinical similarities only and prior to examining any outcomes by comorbidity. We may also include a time-varying binary covariate to record any new diagnosis and/or treatment which occurs after study entry in patients originally free from both diagnosis and treatment, depending on the number of these events. Proportional hazards assumptions will be tested, and time dependent terms will be included if the hazard ratio changes over time (I.e. if the association between neuropsychological disease and risk of severe COVID-19 has changed during the course of the pandemic). A random frailty term will be included to account for similarities amongst patients registered in the same primary care practice. Possible interactions between exposure and age, sex and ethnicity will be considered and tested using a Wald test.

The same methods will be used for secondary analyses in which the main exposure variable will be defined as either the presence of a specific class of neuropsychological disorder or any other neuropsychological disorders or no disorder.

The primary analysis will be used to estimate the hazard ratio of severe SARI outcomes in cohort 2 using the same exposure variables.

If non-proportional hazards are observed in either cohorts 1 or 2, then maximum follow-up time will be capped at 1 year and a time-dependent covariate will be added to the analysis of both cohorts to maintain the comparability of results.

Aim 2.

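### Aim 1 reads treatment once at entry but follows the SARI cohort up to 3.5 times longer than the COVID-19 cohort, and follow-up is equalised only if a proportional-hazards check fails, so the treatment comparison can show a false COVID-SARI difference

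*Protocol*

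**What the plan says.** **Exposure.** Protocol, Definition of exposures (Aim 1): "Our primary exposure is active neuropsychological disease on the study entry date". The treated level of the three-level exposure variable requires "at least two prescriptions for neuropsychological treatments as above within the six months preceding study entry". Both are single readings at entry.

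**Follow-up.** Under Settings, the pandemic window runs from 24 January 2020 to 30 June 2021 and the historical window is "24th January 2015- 23rd January 2020". Under Participants, cohort 2 is open: "the earliest day on which all these conditions were met will be defined as their study entry date". Its follow-up ends as follows: "Patients will be censored at the earliest of first occurrence of deregistration from the GP practise, death from other causes, 24th January 2020" (or the final data extract, if earlier).

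**Comparison.** Statistical Methods, Aim 1: "The primary analysis will be used to estimate the hazard ratio of severe SARI outcomes in cohort 2 using the same exposure variables". Objective 3 sets the two cohorts side by side for prior disease. The antecedent analysis in the opening summary does the same for pre-existing treatments.

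**Safeguards.** Statistical Methods, Aim 1, offers two, both conditional. The first reads "We may also include a time-varying binary covariate to record any new diagnosis and/or treatment which occurs after study entry in patients originally free" of both diagnosis and treatment, and depends on how many such events occur. The second caps follow-up at one year and adds a time-dependent covariate in both cohorts, for comparability, but only if non-proportional hazards are observed in one of them. Sensitivity analyses lists no equal-follow-up analysis for Aim 1. For Aim 2, the Bias section caps all follow-up at one year without any condition.

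**The concern.** A label fixed at entry ages as follow-up runs. Some people recorded as recently treated stop, and some recorded as untreated start. If current treatment drives risk, the entry-based hazard ratio drifts towards 1, and drifts further the longer people are followed. Cohort 2 can be followed 3.5 times as long as cohort 1. Two equal true associations could then be estimated as unequal, with the SARI one weaker, and the gap read as something particular to COVID-19. With about 8.3 million adults (Study Size), even a modest false gap could be estimated precisely enough to look real.

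**Working it through.** **Inputs from the protocol**
- Cohort 1: 24 January 2020 to 30 June 2021 = 523 days = 1.43 years.
- Cohort 2: 24 January 2015 to 23 January 2020 = 1,825 days = 5.0 years at most.
- Ratio: 1,825 / 523 = 3.5.

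The protocol states no effect size, event count or switching rate for Aim 1, so there is no figure of its own to reproduce. Everything below is illustration under stated assumptions.

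**Assumptions.** The true hazard ratio (HR) for current treatment is the same in both cohorts. The baseline hazard is constant. Treated people stop at rate s per year and return to risk 1.0. Untreated people start at rate u per year. Exposure is read on each person's own entry date.

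**Formulae** (mean hazard over follow-up T, relative to untreated)
- Treated at entry: 1 + (HR − 1) × (1 − e^(−sT)) / (sT)
- Untreated at entry: 1 + (HR − 1) × [1 − (1 − e^(−uT)) / (uT)]
- Entry-based HR = first / second

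**Worked case** (HR 2.0, s = 20%, u = 2%)
- Cohort 1, T = 1.43: 1.870 / 1.014 = 1.843
- Cohort 2, T = 5: 1.632 / 1.048 = 1.557
- False ratio: 1.843 / 1.557 = 1.184

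**Treatment results**

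| True HR | Stop / start per year | Cohort 1 | Cohort 2, 5 y | False ratio | Cohort 2, 3.5 y | False ratio |
|---|---|---|---|---|---|---|
| 1.5 | 10% / 1% | 1.461 | 1.377 | 1.061 | 1.410 | 1.036 |
| 1.5 | 20% / 2% | 1.425 | 1.285 | 1.109 | 1.337 | 1.066 |
| 1.5 | 30% / 3% | 1.392 | 1.216 | 1.145 | 1.277 | 1.090 |
| 2.0 | 10% / 1% | 1.918 | 1.744 | 1.100 | 1.812 | 1.058 |
| 2.0 | 20% / 2% | 1.843 | 1.557 | 1.184 | 1.662 | 1.109 |
| 2.0 | 30% / 3% | 1.775 | 1.417 | 1.253 | 1.541 | 1.152 |

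If people who stop stay at 1.25 instead of 1.0, the five-year range at HR 2.0 becomes 1.08 to 1.19.

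**Ever-recorded diagnosis.** It cannot be lost, so s = 0. With u = 1-3% a year, the five-year false ratio is 1.009 to 1.025 at HR 1.5 and 1.017 to 1.049 at HR 2.0.

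**Effect of the optional covariate.** Suppose it handled every new start perfectly (u = 0). The five-year ratio for treatment would still be 1.05 to 1.12 at HR 1.5 and 1.08 to 1.19 at HR 2.0, because stopping remains.

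**Would the cap be triggered?** Approximate the check by a linear trend in log HR over five years in cohort 2. Power is Φ(|b| × √(D × p(1 − p) × var t) − 1.96), with D events, p = 0.2 exposed (assumed) and var t = 25/12. At HR 1.5 the slope b is about −0.033 (10% / 1%) to −0.072 (30% / 3%).
- D = 5,000: the root is √(5,000 × 0.16 × 2.083) = 40.8, so power is Φ(1.35 − 1.96) = 0.27 up to Φ(2.95 − 1.96) = 0.84.
- D = 20,000: the root is 81.6, and power is 0.77 to about 1.00.
- D = 100,000: power is about 1.00.

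**Effect of an unconditional cap.** T = 1 in both cohorts gives the same HR in both (1.446 at HR 1.5 with 20% / 2%), so the false ratio is 1.00.

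**The case against.** The strongest reply is that the protocol already foresees the problem. Decay of an entry-based label is itself a hazard ratio that falls with time, which is what the proportional-hazards check looks for, and the planned response restores equal follow-up. With many events the check would nearly always fire, so large dilution would probably be caught. That stands, and it rules out the stronger reading that the SARI hazard ratios are necessarily diluted more under the plan as written.

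Three other inferences also go too far:
- **Five years for everyone.** Five years is a maximum in an open cohort with individual entry dates and censoring at deregistration. Hence the 3.5-year columns.
- **The same size of error for prior disease in Objective 3.** Treatment-stopping figures do not carry over to an ever-recorded diagnosis, where the effect is small.
- **Bias of this kind in Objective 2.** That objective concerns COVID-19 outcomes only, so unequal dilution against SARI does not bear on it.

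What the reply leaves open is that comparability rests on a test whose power depends on the number of events. Analyses of ICU admission or individual drugs have fewer events than the composite, and could stay uncapped while the main analysis is capped. Stopping treatment is not updated under either safeguard.

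**Conclusion.** The point holds as a conditional weakness, mainly in the treatment comparison. If the cap is not triggered, unequal follow-up alone can produce a false COVID/SARI ratio of about 1.06-1.15 (true HR 1.5) or 1.10-1.25 (true HR 2.0) at five years, about 1.04-1.15 at 3.5 years, and only about 1.01-1.05 for ever-recorded diagnosis. These sizes rest on assumed switching rates, on similar switching in both periods, and on people who stop returning to baseline risk; with residual risk they shrink. The documents do not show that the bias will occur. They show that its prevention depends on a test result, although for Aim 2 the protocol removes the same imbalance unconditionally.

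**What to change.** In Statistical Methods, Aim 1, make the one-year cap in both cohorts unconditional for the COVID-versus-SARI comparison, covering Objective 3 and the treatment comparison in the opening summary. At minimum, add the capped comparison under Sensitivity analyses, to be reported whatever the proportional-hazards check shows. Full follow-up can stay for the within-cohort estimates.

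The cost is follow-up lost from this comparison only: up to 523 − 365 = 158 days in cohort 1 and up to 1,825 − 365 = 1,460 days (four years) in cohort 2. With about 8.3 million adults that is affordable, though the sparsest individual-drug comparisons will lose precision.

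Exposure updated in both directions could be added as a further sensitivity analysis, since the exposure data all come from QResearch. It should be labelled as estimating current rather than pre-existing exposure. It is also open to time-varying confounding, because treatment may be started or stopped as health changes.

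In the same edit, reconcile the fixed 24 January 2015 exposure date given for cohort 2 under Definition of exposures with the individual entry dates under Participants.
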